Study Rationale	
• Child care is a crucial setting for obesity prevention initiatives given environmental influences on eating, and physical activity and the number of US children in some form of child care (12 million; 6 million in center based-program).• National authorities (e.g., Institute of Medicine, American Academy of Pediatrics) and Federal programs (e.g., Child and Adult Care Food Program) recommend that child care programs serve healthy foods, provide adequate time for active play, limit screen time, provide healthy role models, and educate children about healthy lifestyle choices.• Implementation studies are a critical next step in identifying effective approaches for child care-based health promotion and obesity prevention. But existing studies offer little insight into scaling up and implementing these evidence-based practices in child care.• The NAPSACC program is a notable exception, offering a structured process that helps child care programs adopt and implement best practices for obesity prevention. “Go NAPSACC” was created to translate core elements into user-friendly and interactive online tools that child care programs can use independently.• While pilot studies suggest that Go NAPSACC retains its effectiveness in improving their practices, further study is needed to confirm its effectiveness and examine strategies to enhance its implementation.
Study Objective(s)	
This study will evaluate the impact of Go NAPSACC on child care center practices as well as the adoption, implementation, and maintenance achieved with Go NAPSACC when using basic vs. enhanced implementation models.
 
• Primary Aim: Aim 1. Compare Basic vs. Enhanced Go NAPSACC’s impact on centers’ implementation of healthy weight practices.• Secondary Aims: Aim 2. Evaluate adoption, implementation, and maintenance of Go NAPSACC; Aim 3. Examine how organizational factors predict implementation; Aim 4. Calculate incremental cost-effectiveness ratio in terms of environmental change; Aim 5. Compare impact on children’s diet quality and physical activity at child care.

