Items on the EPAO-SR will be used to assess compliance with nutrition and physical activity best practices, and ultimately, to calculate a combined nutrition and physical activity score. Nutrition best practices will be categorized into six domains: foods provided, beverages provided, feeding practices, the feeding environment, nutrition training and education, and nutrition policy. Physical activity best practices were categorized into six domains: active play and screen time provided, the indoor play environment, the outdoor play environment, physical activity and screen practices, physical activity training and education, and physical activity and screen policy. For each best practice, the EPAO-SR will be used to score compliance, ranging from 0 to 3; a score of “0” indicated non-compliance with the best practice, “1”, and “2”, represented partial compliance, while “3” indicated full compliance with the best practice. Best practice compliance scores within each domain will be averaged and then summed to create an overall nutrition (range = 0–18) and an overall physical activity score (range = 0–18). Finally, these overall nutrition and physical activity scores will be summed to create a single, combined nutrition and physical activity score (range = 0–36). Higher scores indicate compliance with a greater number of best practices, which translates to higher-quality environments.

Contextual factors influencing implementation. As recommended by the CFIR framework (2), the most salient constructs were identified based on barriers identified in previous NAPSACC studies (3–7) and our extensive and ongoing work implementing Go NAPSACC. Prioritized constructs were operationalized for the child care setting and a nutrition and physical activity intervention. Self-administered surveys completed by directors, teachers, and coaches at baseline and postintervention will be used to assess these constructs. Survey items draw from existing scales, including Fernandez’s Inner Setting Survey (ISS) (8), the Organizational Readiness for Change (ORC) survey (9,10), and Seward’s Theoretical Domains Framework Questionnaire (TDFQ) for child care (11–13). The ISS and ORC use a 5-point Likert scale, while the TDFQ uses a 7-point Likert scale (where 1 = strongly disagree and 5 or 7 = strongly agree).

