1.2 Secondary Objective

- Aim 2. Evaluate adoption, implementation, and maintenance of Basic vs. Enhanced Go NAPSACC.
 - *Hypothesis 2.* Reach, adoption, implementation, and maintenance (as defined by RE-AIM) will be higher among centers receiving Enhanced Go NAPSACC compared to centers receiving Basic Go NAPSACC.
- Aim 3. Examine how organizational factors predict implementation under Basic vs. Enhanced conditions.
 - *Hypothesis 3.* Positive organizational factors (as defined by CFIR), such as communication, culture, implementation climate, and readiness, will enhance implementation of Go NAPSACC.
- Aim 4. Calculate incremental cost-effectiveness ratio of Basic vs. Enhanced Go NAPSACC in terms of changing centers' environments.
 - *Hypothesis 4.* Both Enhanced and Basic Go NAPSACC will be cost-effective in terms of costs per outcome achieved, but Enhanced Go NAPSACC will be more efficient than Basic Go NAPSACC.
- Aim 5. Compare Basic vs. Enhanced Go NAPSACC's impact on children's diet quality and physical activity at child care.
 - *Hypothesis 5.* Children enrolled at centers receiving Enhanced Go NAPSACC will have higher diet quality and spend more time in physical activity while at child care compared to children at centers receiving Basic Go NAPSACC.

2 INVESTIGATIONAL PLAN (brief overview)

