4.4 Statistical Methods

Primary Aim:

Our primary analyses will test the hypothesis under the intent-to-treat (ITT) principle using Generalized Linear Mixed Models (GLMM) that account for the clustering of child care centers within regions/TA. The primary GLMM will include a random intercept for region (b_0) and fixed effects for the baseline value of the primary outcome (β_1) and the intervention (β_2) to test if the differences in mean changes in primary outcomes is zero, where β_0 is the fixed intercept, and e is error.

$$\text{Change in Primary Outcome}_{12m} = \beta_0 + \beta_1 \text{ Primary Outcome}_{\text{baseline}} + \beta_2 \text{ Intervention} + b_0 + e$$

To further explore the intervention effect, we will examine: 1) baseline covariates relevant to change in EPAO scores; 2) interaction between treatment group and other covariates; and 3) completers only. Baseline demographics and EPAO scores will be compared between centers with and without follow-up measures to inspect for potential bias.

Secondary Aims:

Analysis for secondary aims will use statistical models like those applied for primary analysis. Generalized Linear Mixed Models (GLMM) that account for the clustering of child care centers within regions/TA under the intent to treat principle will be utilized. The primary GLMM will include a random intercept for region and fixed effects for the baseline value of the outcome and the intervention. Interaction terms will be added to models where needed. Specifics relevant to aims 2-5 include:

Aim 2. Data used to evaluate adoption, implementation, and maintenance of Basic vs. Enhanced Go NAPSACC will be compiled from the Go NAPSACC registration reports and activity reports (Center and TA). Outcomes computed from these reports include: registration, account initiation, first self-assessments, selection of goal, creating action plans, post cycle self-assessment, TA contacts, and TA implementation activities.

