Aim 3. Section 1.4 includes a summary of the organizational factors outcomes that will be assessed. In short Fernandez's CFIR Inner Setting: Culture, Culture Stress, Culture Effort, Implementation Climate, Leadership Engagement, and Available Resources along with TCU's Organizational Readiness for Change: Networks and Communications and Access to Knowledge and Information will be collected from surveys completed by directors, teachers, and TA coaches. Organizational outcomes will be examined as moderators of the intervention effects in statistical models. Both continuous and categorical (quartiles) moderation effects will be tested.

Aim 4. Details about computing program cost can be found in section 1.4. The average incremental cost of delivering Enhanced Go NAPSACC will be divided by the incremental change in effectiveness (relative to Basic Go NAPSACC) to quantify the incremental cost-effectiveness ratio. The Incremental Cost-Effectiveness Ratio includes costs over the time period of the study and effectiveness measured by the unit increase in EPAO score. Standard GLMM models will be used to compare cost ratios between intervention groups.

Aim 5. Diet and activity information from the EPAO-sr (see section 1.4) will be used to diet quality of the food served to children and the physical activity time provided. Food and meal reporting will be used to summarize center-level dietary intake and to calculate diet quality (Healthy Eating Index 2015), while daily activities reporting will be used to summarize the activity levels of children. Outdoor time, active indoor time, vigorous minutes, and teacher ratings of activity level will be used to calculate an activity level index. Analysis and statistical models used to evaluate this aim will be nearly identical to those for primary analysis.

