4.5 Sample Size and Power

The primary outcome for this study is change in centers' implementation of nutrition and physical activity evidence-based best practices the Enhanced and Basic Go NAPSACC arms based on scores

from the EPAO. Power calculations in Table specify the sample size needed to detect significant differences in changes with 80% power and an alpha of 0.05. An effect size of 0.6 was used, representing a conservative estimate based on published NAPSACC studies (with effects ranging from 0.4 to 1.1). An ICC of 0.001 is included based on our Go NAPSACC pilot (31 centers from 3 regions), which found negligible correlation (> 0.001) in EPAO scores between centers located within the same region. Cluster size is estimated at 10-15 centers per region. While regional TA providers likely have a larger caseload, only a sample of centers will be recruited to take part. Based

on these specifications, a sample size of 88 centers is needed detect an effect size of 0.60 with 80% power and a 0.05 level of significance. The final sample size of 97 centers allows for 10% attrition, which should be more than sufficient based on previous work with child care centers that has demonstrated low center attrition ($<10\%$). Depending on the number and capacity of TA providers, we will need to recruit approximately 8 TA providers, each of which will need to recruit 12-13 child care centers.

Power calculations

alpha	power	effect size	ICC	cluster size	suggested sample size	# of clusters
0.05	0.2	0.5	0.001	10	126.7	12.7
0.05	0.2	0.6	0.001	10	88.0	8.8
0.05	0.2	0.7	0.001	10	64.6	6.5
0.05	0.8	0.5	0.001	15	127.3	8.5
0.05	0.8	0.6	0.001	15	88.4	5.9
0.05	0.8	0.7	0.001	15	65.0	4.3

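### The only analysis named for Aim 3 tests whether organizational factors moderate the arm effect, which does not test Hypothesis 3 that they enhance implementation

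*Combined protocol and SAP*

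**What the plan says.** Hypothesis 3 (section 1.2) states that positive organizational factors, "such as communication, culture, implementation climate, and readiness, will enhance implementation of Go NAPSACC". It makes no comparison between arms. The synopsis states the aim in the same spirit: "Aim 3. Examine how organizational factors predict implementation". Section 1.2 words the aim itself slightly differently: "Examine how organizational factors predict implementation under Basic vs. Enhanced conditions".

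The analysis is in section 4.4. The general rule for secondary aims is: "The primary GLMM will include a random intercept for region and fixed effects for the baseline value of the outcome and the intervention". Interactions may be added as needed. For Aim 3 specifically, eight constructs are listed, followed by "Organizational outcomes will be examined as moderators of the intervention effects in statistical models" and "Both continuous and categorical (quartiles) moderation effects will be tested". No test of a construct's own association with implementation is named, either overall or within arm. The implementation outcome for Aim 3 is not named either.

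On timing, section 1.4 says: "Self-administered surveys completed by directors, teachers, and coaches at baseline and postintervention will be used to assess these constructs". The Aim 3 text in section 4.4 does not say which of the two measurements serves as the moderator.

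**The concern.** A moderation test asks whether the slope of implementation on a factor differs between Basic and Enhanced. Hypothesis 3 asks whether that slope is positive. The two come apart in the simplest case in which the hypothesis is true: a factor that helps centers equally under both models has a positive slope and no interaction. The planned test then has nothing to find, and a larger sample would not help.

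Where the slopes do differ, the interaction is estimated much less precisely than the overall association. The trial could therefore finish with useful information on Hypothesis 3 and no prespecified analysis that reports it.

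Timing adds to this. Enhanced is meant to build center capacity (Introduction) and includes a readiness check with support tailored to its results (section 3.2). A construct measured after the intervention could be changed by arm, and an interaction with it would be hard to interpret.

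**Working it through.** **Inputs.** Alpha 0.05, 80% power, effect size 0.6, ICC 0.001, cluster size 10 to 15 and 88 centers come from section 4.5. The 26 coaches are the follow-up count in the synopsis. Two arms randomized by coach is from section 2.1. The allocation ratio is not stated, so an equal split of centers is an assumption.

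**1. The plan's own figure.** Section 4.5 says "a sample size of 88 centers is needed detect an effect size of 0.60 with 80% power and a 0.05 level of significance". The total before clustering is 4 × ((1.960 + 0.842)/0.6)² = 87.2. Multiplying by 1 + (m − 1) × 0.001 gives 88.0 at m = 10 and 88.4 at m = 15. Both match the table, and the match shows that a two-sided 0.05 was used. This figure is for the primary arm comparison; the plan gives none for Aim 3.

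**2. Variance of the two estimates.** Take N centers, residual variance s², factor variance sx² in each arm, and a share p of centers in one arm.

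- Pooled slope: s² / (N sx²).
- Slope difference between arms: s² / (N sx² p(1 − p)).

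The ratio of information is p(1 − p): 0.25 at 1:1, 0.24 at 60:40 and 0.21 at 70:30. At 1:1 the standard error of the slope difference is twice that of the pooled slope.

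**3. Power at the same size.** A pooled slope with 80% power lies 2.802 standard errors from zero. As an interaction of the same size it lies 2.802/2 = 1.401 standard errors from zero, and Φ(1.401 − 1.960) = 0.288, about 29%.

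**4. In SD units with 88 centers.** The smallest slope detectable with 80% power is 2.802/√88 = 0.30 SD of outcome per SD of factor. The smallest detectable slope difference is twice that, 0.60. Over an assumed range of true sizes:

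| True size | Power, pooled slope | Power, slope difference |
|---|---|---|
| 0.2 | 47% | 15% |
| 0.3 | 80% | 29% |
| 0.4 | 96% | 47% |
| 0.5 | 99.7% | 65% |

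**5. When Hypothesis 3 is true equally in both arms.** This was simulated with 88 centers, 26 coaches split equally, ICC 0.001, 4,000 trials and least-squares fits adjusted for arm and baseline.

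| Slope in each arm | Pooled-slope test significant | Interaction test significant |
|---|---|---|
| 0.3 | 77% | 4.7% |
| 0.5 | 99% | 4.8% |

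The interaction column is the false-positive rate. Simulated variance ratios, over these and two unequal-slope settings, were 0.246 to 0.252, in line with step 2.

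**6. Quartiles.** Crossing quartiles with arm leaves 88/(4 × 2) = 11 centers per cell.

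**The case against.** The strongest reply is that section 1.2 words Aim 3 by condition, so moderation is a legitimate planned analysis. That stands. A reader might infer that moderation is the wrong analysis and should go; the aim's wording does not support this. What is missing is a test of Hypothesis 3 beside it.

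A second reply is that an interaction model normally contains the factor's own term, so the association is estimated anyway. This is partly right. A reader might go further and say that this coefficient is only the reference-arm slope. That is true under 0/1 arm coding but not in general. In one simulated data set with arm slopes 0.148 and 0.609, the coefficient was 0.148 under 0/1 coding and 0.379 under −0.5/+0.5 coding, the average of the two. The plan states neither the coding nor that this term tests Hypothesis 3, so the gap remains.

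A third reply points to the baseline covariates that section 4.4 allows under the primary aim. Those are for exploring the intervention effect, and organizational factors are not named among them.

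Three other strong readings are not supported:

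- That Aim 3 will be declared negative if no interaction is found. The plan gives no decision rule for Aim 3, so this is a risk only.
- That post-intervention values will be used as moderators. Section 1.4 describes collection; the time point for analysis is simply left open.
- That eight constructs in two forms make 16 independent tests. The continuous and quartile forms use the same scores, so an error rate computed that way is too high.

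**Conclusion.** The point holds. The analysis named for Aim 3 does not test Hypothesis 3, and it cannot support the hypothesis when the factors help both arms alike. That conclusion needs no assumption about effect size or sample size.

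The precision result is conditional. The fourfold variance, and the drop from 80% to about 29% power, assume near-equal arms, equal factor spread and residual variance in each arm, a factor measured at center level, a continuous outcome, and a slope difference as large as the pooled slope. The plan claims no such size for the interaction. Three of the eight constructs are also asked of coaches (Appendix, Table 2); for coach-reported values the effective sample is the number of coaches, and both tests lose precision. If the Aim 3 outcome is a yes/no website marker, the figures do not carry over directly.

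The effect is confined to a secondary aim. The primary comparison is untouched.

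**What to change.** Revise the Aim 3 text in section 4.4 as follows.

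1. Name the implementation outcome or outcomes, whether EPAO-SR scores as in Aim 1, website markers as in Aim 2, or both.
2. State as the test of Hypothesis 3 the pooled association of each construct with that outcome, adjusted for arm, the baseline outcome where one exists, and the clustering term.
3. Keep the factor-by-arm interaction as a separate analysis addressing the by-condition part of the aim.
4. Specify baseline construct values for both analyses.
5. Test the continuous form and use quartiles for display.

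The data and model family are those already planned, so the main cost is SAP wording plus the decision on the outcome, which has to be made in any case. The downside is that the quartile tests become descriptive. Eight constructs would still be tested, and this change does not settle how multiplicity across them is handled.

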Number Of Subjects	
TA Coaches: BL n = 27; FU n = 26
 
Child Care Centers: BL n = 97; FU n = 88
 
Child Care Providers: BL n = 257; FU old n = 139, FU new n = 82

Study Duration	Each subject's participation will last approximately 14 months; 1 month for baseline data collection, 12 months of intervention, and 1 month of follow up data collection. The entire study is expected to last approximately 3 ½ years.
Study Phases	
(1) Screening and recruitment: During this phase we will identify and recruit TA coaches and get lists of the centers they serve. Centers will be screened for eligibility and recruited randomly. After a director and teachers consent, baseline data collection will be completed (2) Intervention: After baseline measurement, TAs will be randomly assigned to Basic or Enhanced Go NAPSACC implementation and the 12-month intervention will proceed (3) Follow-Up: After the 12-month intervention, follow up measures and process evaluations will be completed.

Efficacy Evaluations	
 • Primary Objective 
 ○ Aim 1. Compare intervention impact on implementation of healthy weight practices. 
 ▪ EPAO-SR Nutrition and Physical activity environment scores. • Secondary Objectives 
 ○ Aim 2. Evaluate adoption, implementation, and maintenance by group. 
 ▪ Percent of centers creating accounts, completing self-assessments, selecting goals, and creation of action plans will be captured by the Go NAPSACC website and extracted using the registration and detailed activity reports. ○ Aim 3. Examine how organizational factors predict implementation. 
 ▪ Surveys completed by directors, teachers, and TA coaches. ▪ Fernandez's CFIR Inner Setting: Culture, Culture Stress, Culture Effort, Implementation Climate, Leadership Engagement, and Available Resources. ▪ TCU's Organizational Readiness for Change: Networks and Communications and Access to Knowledge and Information. ○ Aim 4. Calculate incremental cost-effectiveness ratio for environment change. 
 ▪ Costs include TA coaches time and any resources required to train and support centers for 12 months. Costs will be tracked in the TA Activity and

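### Aim 4 defines the ICER correctly, but its only stated inference, a GLMM on undefined cost ratios, cannot test relative efficiency; no ICER interval is planned and the EPAO denominator is ambiguous

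*Combined protocol and SAP*

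**What the plan says.** Section 4.4 (Statistical Methods), Aim 4, gives the ICER: "The average incremental cost of delivering Enhanced Go NAPSACC will be divided by the incremental change in effectiveness", relative to Basic, with "effectiveness measured by the unit increase in EPAO score". The only inferential statement follows: "Standard GLMM models will be used to compare cost ratios between intervention groups".

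The parts of the document that bear on this are:

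- **Hypothesis 4** (Section 1.2, Secondary Objective) has two halves. Both arms are expected to be cost-effective in cost per outcome achieved, and "Enhanced Go NAPSACC will be more efficient than Basic Go NAPSACC".
- **Costs** (Synopsis, Efficacy Evaluations, Aim 4): "Costs include TA coaches time and any resources required to train and support centers for 12 months". They are to be turned into a total cost for each center and combined with the Aim 1 EPAO-SR outcomes.
- **Aim 1 outcomes** (Synopsis, Efficacy Evaluations): "EPAO-SR Nutrition and Physical activity environment scores", which are two scores.
- **EPAO scoring** (Section 1.4): nutrition and physical activity each run from 0 to 18, and "these overall nutrition and physical activity scores will be summed to create a single, combined nutrition and physical activity score", running from 0 to 36.
- **Default for secondary aims** (Section 4.4): models like the primary one. "The primary GLMM will include a random intercept for region and fixed effects for the baseline value of the outcome and the intervention".

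The document mentions no confidence interval for the ICER, no resampling or Fieller method, no net-benefit analysis and no value placed on an EPAO point.

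**The concern.** Hypothesis 4 is directional and Section 4.4 promises a between-group comparison, so Aim 4 is more than descriptive. The analyst needs a quantity that reflects both cost and effect, exists for each arm, and comes with a standard error. The sentence on cost ratios does not supply one.

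If it is followed literally, Aim 4 could end with an ICER that has no interval, beside a test that is either silent on efficiency or numerically unstable. The headline cost per EPAO point would also depend on which score is picked at analysis.

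**Working it through.** **1. The plan's own figure.** Aim 4 has no sample size, so the illustrations use the primary one (Section 4.5). With two-sided α = 0.05, power 0.80, effect 0.6 SD, ICC 0.001 and cluster size m, total = 4 × ((1.960 + 0.842)/0.6)² × [1 + (m − 1) × 0.001]. This gives 87.99 for m = 10 and 88.43 for m = 15, matching the tabulated 88.0 and 88.4. That is 44 centers per arm.

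**2. Assumptions.** The document gives no costs and no within-arm change. I assume an SD of change of 1, a Basic mean change of 0.5 or 1.0 SD, Enhanced 0.6 SD higher (Section 4.5), Basic cost 1, and Enhanced cost 1.5 times Basic unless stated. Centers are independent and costs are treated as known, except in step 7.

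**3. Reading A: compare the ICER between groups.** The ICER is (cost E − cost B)/(change E − change B), one number for the trial. There is nothing to compare between arms.

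**4. Reading B: GLMM on cost per center.** The tested ratio is 1.5 whatever the effect. With a Basic change of 0.5:

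| | Cost per SD gained |
|---|---|
| Basic | 1/0.5 = 2.0 |
| Enhanced, no extra effect | 1.5/0.5 = 3.0 |
| Enhanced, +0.6 SD | 1.5/1.1 = 1.36 |

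The same cost ratio fits either ordering. Enhanced is cheaper per point only if its cost ratio is below 1.1/0.5 = 2.2 (Basic 0.5) or 1.6/1.0 = 1.6 (Basic 1.0).

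**5. Reading C: GLMM on each center's cost divided by its change.** The ratio is undefined at zero change and negative when a center worsens. P(change ≤ 0) in Basic is Φ(−0.5) = 0.309 or Φ(−1.0) = 0.159. In simulation, the mean of 44 Basic center ratios had a 95% range of about −13 to 14 (true cost per SD 2.0) or −9 to 10 (true 1.0). At cost ratio 1.5 the test favored Enhanced in 0.2% of trials, and the estimate pointed to the wrong arm in 59–60%.

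**6. Reading D: arm-level mean cost over mean change.** This is coherent. The Basic 95% range is 1/(0.5 ± 1.96/√44) = 1.26 to 4.89, or 1/(1.0 ± 1.96/√44) = 0.77 to 1.42. It still needs a joint, delta-method or resampling step that is not planned. When both mean changes are positive, Enhanced is cheaper per point exactly when L = cost E × change B − cost B × change E is below zero. With SE(L) = √((1.5² + 1²)/44) = 0.272:

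- Basic 0.5: L = 0.75 − 1.10 = −0.35, z = 1.29, power Φ(1.29 − 1.96) ≈ 25%, wrong direction Φ(−1.29) ≈ 10%.
- Basic 1.0: L = 1.50 − 1.60 = −0.10, z = 0.37, power ≈ 6%, wrong direction ≈ 36%.

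**7. Interval for the ICER.** A 95% Fieller interval is unbounded whenever the EPAO difference is not significant at 5%. With 88 independent centers that is 1 − 0.804 ≈ 20% of trials at effect 0.6, 53% at 0.4 and under 0.1% at 1.1. Simulating coach means at effect 0.6 (coaches minus 2 degrees of freedom, EPAO ICC 0.001 or 0.05) gave 35–51% with 8 coaches (Section 2.3) and 23–29% with 26 (Synopsis, follow-up count).

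**8. Choice of score.** Let the incremental cost be C and the combined gain g. An even split gives C/(0.5g), twice C/g, on either single score. An 80/20 split gives C/(0.8g) = 1.25 times and C/(0.2g) = 5 times.

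**The case against.** Four points on the other side have force.

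- **The denominator is not absent.** Section 4.4 names the EPAO score and the Synopsis ties the ICER to the Aim 1 outcomes. A reader might infer that no denominator was specified. The text supports only that it is ambiguous among documented scores: singular in Section 4.4, two scores in the Synopsis, a third in Section 1.4.
- **The default model can be adapted.** A reader might infer that the GLMM cannot be fitted because cost has no baseline value. Section 4.4 asks for similar models, not identical ones, and dropping that term is ordinary practice. The Synopsis also supplies a cost per center that a GLMM can take. Neither point brings effect into the comparison.
- **Center-level ratios are not stated.** The instability in step 5 shows what to rule out. It does not show what the investigators intend.
- **Low power is partly a matter of method.** A reader might infer that no arm-level test is worth running. A delta-method test gave 3–6% at cost ratio 1.5, but the linear contrast of the same hypothesis gives about 25% or 6%.

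It is also fair to say that an ICER reported without uncertainty is inferred from silence; an analyst could add an interval. That would still be an unplanned choice.

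**Conclusion.** The concern holds, as an inexpensive improvement to a secondary aim. The ICER formula is right. The inference attached to it is undefined, and the readings a standard GLMM fits directly either ignore effect or behave badly near zero change. No interval is planned, and the score choice can change cost per point by a factor of 2 under an even split (1.25 or 5 under 80/20).

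The sizes rest on assumed costs, mean changes and variances, because the document gives none. Nothing here touches the ICER formula or the primary analysis, and no decision rule depends on Aim 4. The first half of Hypothesis 4, that both arms are cost-effective, can only be described, since there is no untreated arm and no threshold.

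**What to change.** Replace the sentence on cost ratios with wording such as:

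> Incremental cost and incremental EPAO change will be estimated on the same centers with the same covariates, in models clustered by TA coach with baseline EPAO as a covariate. The ICER will be formed from these two estimates, never from center-level ratios, with a 95% Fieller interval that uses their covariance and coach-level degrees of freedom, solved over all values and reported as unbounded when it is. The combined EPAO score (0–36) is the main denominator; results for the nutrition and physical activity scores are also reported. Relative efficiency under Hypothesis 4 will be tested as arm-level cost per point by the linear contrast (Enhanced mean cost × Basic mean change) − (Basic mean cost × Enhanced mean change), with coach-clustered standard errors. Whether both arms are cost-effective will be described, not tested.

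Clustering by coach follows the unit of randomization in Section 2.1. The contrast ranks cost per point only when both mean changes are positive, and the text should say so.

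Incremental net benefit over a stated range of values per point may be added, with a note that it is a different estimand and can favor the other arm. At cost ratio 2 and Basic change 1.0 SD, Basic is cheaper per point (1/1.0 = 1.00 against 2/1.6 = 1.25), yet net benefit favors Enhanced at any value above (2 − 1)/0.6 = 1.67 per SD.

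The cost is SAP wording and modest analysis on data already planned. Power stays limited, and the ICER interval will often be unbounded, especially with only 8 coaches.
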